
Sample Size

We estimate the sample size required to answer the research question to be 50 participants.

Interventions and Interactions

Once both informed consent and enrollment have been verified, initial evaluation by the PI will be conducted on participants, and baseline assessments will be performed. The assessments include:

- Documentation of participant age at enrollment along with information on sex/gender, race, and ethnicity to ensure the study involves Inclusion of Individuals across the Lifespan
- History and physical exam
- Calculated BMI
- Documentation of referral patterns (PCP, self, or other referral)
 - If from PCP or other, documentation of what information/work-up was provided (e.g. told they have “heel spur”, given NSAIDs, exercises, etc.)
- Clinical confirmation/diagnosis of plantar fasciitis (pain at medial calcaneal tubercle)
- Dolorimeter readings of PPT # (pressure algometer)
- Documentation of subjective reporting of first-step pain (yes/no)
- Foot posture score
- Heel tenderness score
- Initial X-ray (notation and measurement of heel spur) of the symptomatic foot/heel will be performed, if not already completed
- Initial diagnostic musculoskeletal US (PF thickness and echogenicity; fat pad thickness)
- Patient completed baseline self-assessment of both “general heel pain” and “first step pain” (VAS PROM)
- Patient completed baseline self-assessment of foot function (FFI PROM)

At this point, the patient will be block allocated to their study arm, having been randomized in a double-blind fashion by the clinical coordinator. This individual will facilitate safe record-keeping and the processes required to maintain the double-blind design of this study. We will specifically conduct the study in a permuted block design to ensure a 1:1 ratio for the two treatment intervention groups. The study arms are as follows:

- Group 1 - CSI/LA injection
- Group 2 - LA/Saline injection

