A nurse or staff member will open a previously prepared and sealed opaque envelope (prepared beforehand by the clinical coordinator) labeled with the participant ID of the patient, which will be unique to the individual and different from their MRN. In this envelope, they will discover the patient's assigned treatment arm. The nurse or staff member will then prepare the syringe with the assigned treatment arm. Once the syringe is filled with the designated substance, the syringe will be wrapped with opaque tape or dark Coban wrap to conceal the contents in the

syringe for both the PI and study participant. The participant's skin will be steriley prepped with alcohol.

The PI will then administer the injection using an infracalcaneal needle peppering technique as follows:

1. The hypodermic needle is inserted using infracalcaneal injection approach.
2. The hypodermic needle is withdrawn while at the same depositing injectate.
3. The hypodermic needle is redirected without emerging from the skin.

The PI will perform steps 1-3 standardly 20-25 times. Following the completion of the injection and clinical observation, the patient will receive home care and follow-up instructions which will include the standardized teaching of 3 exercises (calf stretching, plantar fascia specific stretching, and plantar fascia loading exercise). Patients will be sent home with an exercise diary to record when and if they complete the instructed exercises with directions to bring the diary to the next visit. Patients will receive 1 phone call between this visit and the next to check in on their exercise progress and remind them to complete the exercise diary.

The patient will be seen at follow-up visit #1 for evaluation and management 2 weeks post-treatment intervention. At this visit, the following assessments will be completed:

- History and physical exam
- Patient self-assessment of both "general heel pain" and "first step pain" (VAS PROM)
- Patient self-assessment of foot function (FFI PROM)
- Dolorimeter readings of PPT # (pressure algometer)
- Heel tenderness score
- Review of the exercise diary

A new exercise diary will be given to the patient. The recommended exercises will be instructed again. Patients will be encouraged to bring the diary to their next visit. To increase compliance, patients will receive 1 phone call to check in on their exercise progress and remind them to complete the exercise diary.

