The patient will return for follow-up visit #2 for evaluation and management 4 weeks post-treatment intervention. At this visit, the following assessments will be completed:

- History and physical exam
- Patient self-assessment of both "general heel pain" and "first step pain" (VAS PROM)
- Patient self-assessment of foot function (FFI PROM)
- Dolorimeter readings of PPT # (pressure algometer)
- Heel tenderness score
- Review of the exercise diary

A new exercise diary will be given to the patient. The recommended exercises will be instructed again. Patients will be encouraged to bring the diary to their next visit. The patient will be called 1 time to remind them to complete their exercise diary between visits.

The patient will return for follow-up visit #3 for evaluation and management 8 weeks post-treatment intervention. At this visit, the following assessments will be completed:

- History and physical exam
- Patient self-assessment of both "general heel pain" and "first step pain" (VAS PROM)
- Patient self-assessment of foot function (FFI PROM)
- Dolorimeter readings of PPT # (pressure algometer)
- Heel tenderness score

- Review of the exercise diary

A new exercise diary will be given to the patient. The recommended exercises will be instructed again. Patients will be encouraged to bring the diary to their next visit. The patient will be called 1 last time to remind them of their exercise diary and encourage them to complete it.

The follow-up visit #4 will be the final study visit. This visit will occur 12 weeks post-treatment intervention. At this visit, the following assessments will be completed:

- History and physical exam
- Patient self-assessment of both “general heel pain” and “first step pain” (VAS PROM)
- Patient self-assessment of foot function (FFI PROM)
- Dolorimeter readings of PPT # (pressure algometer)
- Heel tenderness score
- Review of the exercise diary
- Final diagnostic musculoskeletal US (PF thickness and echogenicity; fat pad thickness)
- Exit survey

Evaluation Schedule Summary

Procedures	Screening -42 to -1 days	Injection day 0	Week 2 +/- 3 days	Week 4 +/- 3 days	Week 8 +/- 3 days	Week 12 +/- 3 days
Review Study Procedures, Informed Consent, and Privacy Authorization	x	x				
Eligibility Criteria for Study Entry	x	x				
Patient Demographics	x					
Patient Medical/Surgical History	x	x				
Height, Weight, and Vital Signs	x	x	x	x	x	x
Foot & Ankle Physical Exam	x	x	x	x	x	x

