Presentation of Exercise Therapy (targeted stretching and strengthening)	x	x	x	x	x	x
Clinical Observation	x					
X-ray of Affected Foot	x					
Ultrasound of Affected Foot	x					x
Randomization		x				
Study Therapeutic Treatment Intervention (infracalcaneal needle peppering injections)		x				
Evaluation of Injection Site		x	x	x	x	x

Subject Self-Assessments - VAS PROM (for both general heel pain and first step pain) - FFI PROM	x	x	x	x	x	x
Exercise Diary & Instruction of the 3 Exercises		x	x	x	x	x
Foot Posture	x	x				
Heel Pressure Threshold using Dolorimeter	x	x	x	x	x	x
Heel Tenderness Score	x	x	x	x	x	x
Exit Survey						x

*Not on schedule: reminder phone call between study visits to encourage exercise diary completion and compliance.

Outcome Measure(s)

Patient Assessments

- Heel Tenderness VAS PROM
- First Step Pain VAS PROM
- FFI PROM
- Exercise Diary
- Exit Survey at completion of study

Physician Assessments

- Baseline and subsequent foot and ankle physical exam, heel pressure threshold, and heel tenderness score
- X-ray and ultrasound imaging
 - Our research team will be the first to examine musculoskeletal ultrasound imaging obtained both before and after an infracalcaneal peppering injection in participants with chronic plantar fasciitis. Musculoskeletal ultrasound has become more established in the medical literature as a reliable objective measure of plantar fasciitis, with thickness measurements >4.0mm correlating with clinical symptoms (40). Musculoskeletal ultrasound's utility here would enable our investigators to assess for any quantifiable tissue changes associated with our intervention.

Patient Retention

Every effort will be made to retain patients in the study to ensure complete data collection. During the study consent process, potential study participants will be educated regarding the importance of full participation in all visits. Patients will be reminded of their upcoming appointment via phone call or email. Patients will also be reminded about their follow-up visits at all clinic visits.

Patient/study participant compensation will occur at certain study visits. Study participants will receive a paid total of \$100.00 if all scheduled study visits are completed.

Study Visit #1 – injection day	\$20.00
Study Visit #2 – 2 weeks post-treatment intervention	No payment. Next payment at 4-week follow-up study visit (visit #3).
Study Visit #3 – 4 weeks post-treatment intervention	\$40.00

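### The dated schedule puts the only pre-injection ultrasound at screening, 1 to 42 days before injection, and the narrative gives no day, so the before-after tissue change can include time before the intervention

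*Combined protocol and SAP*

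**What the plan says.** The Evaluation Schedule Summary has six visit columns, from "Screening -42 to -1 days" through injection day 0 to week 12 with a window of 3 days either side. The row "Ultrasound of Affected Foot" is ticked in the first and last columns only. VAS, FFI, dolorimeter threshold and heel tenderness score are ticked at screening and again on day 0.

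The narrative under Interventions and Interactions includes, in its list of baseline assessments, "Initial diagnostic musculoskeletal US (PF thickness and echogenicity; fat pad thickness". It then continues: "At this point, the patient will be block allocated to their study arm". Neither statement carries a day.

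Under Outcome Measure(s), the team says it will be the first to compare ultrasound before and after this injection technique, and that the imaging will let it "assess for any quantifiable tissue changes associated with our intervention".

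Two schedule rows concern exercise. "Presentation of Exercise Therapy (targeted stretching and strengthening" is ticked from screening onwards; "Exercise Diary & Instruction of the 3 Exercises" starts on day 0.

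**The concern.** A before-after measure describes an intervention best when its first reading is taken immediately before that intervention. As scheduled, the ultrasound baseline can be up to six weeks old at injection, whereas the other repeated outcome measures have a fresh day-0 value. Any change in fascia thickness, echogenicity or fat pad between the screening scan and the injection would be counted in the change linked to the intervention. The length of that gap would also differ between participants.

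Both arms are peppered, so the randomised contrast says nothing about peppering itself. The within-participant change is the only ultrasound evidence on it, and that is the quantity an early baseline blurs. The Analytical Plan names no ultrasound analysis and no adjustment for the gap between scan and injection.

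What is at stake is limited: the clarity of a supporting imaging measure in a pilot of 50 participants.

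**Working it through.** The plan states no figure for the scan interval, so there is none to reproduce. The check uses only the visit windows in the Evaluation Schedule Summary.

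**Inputs**
- First scan: 1 to 42 days before injection (screening column).
- Final scan: week 12 ± 3 days, that is 84 − 3 = 81 to 84 + 3 = 87 days after injection.
- The ultrasound row as read has six cells (tick, four blanks, tick), matching the six visit columns. The reading does not depend on a broken table.

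**Formulas**
- Scan-to-scan interval = days before injection + days after injection.
- Pre-injection share = days before ÷ (days before + days after).

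**As scheduled**
- Shortest interval: 1 + 81 = 82 days. Longest: 42 + 87 = 129 days. Spread: 129 − 82 = 47 days.
- Smallest share: 1 ÷ (1 + 87) = 1/88 = 1.1%.
- Largest share: 42 ÷ (42 + 81) = 42/123 = 34.1%.
- With a 42-day gap and a final visit at exactly week 12: 42/126 = 33.3%.

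**With a day-0 scan**
- Interval: 81 to 87 days. Spread: 6 days. Share: 0%.

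**With a scan on day −7 to 0**
- Interval: 81 to 7 + 87 = 94 days.
- Largest share: 7 ÷ (7 + 81) = 7/88 = 8.0%.

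These are shares of elapsed time, not of tissue change. The documents give no rate of change in fascia or fat pad and no typical gap, so the change before injection cannot be calculated. The background text offers no direction either: it reports that most experts regard the condition as self-limiting, but also that the long-term evidence is equivocal.

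**The case against.** **The tick may be a slip.** The narrative moves straight from the baseline list to allocation, and the payment table under Patient Retention numbers injection day as the first study visit. Both fit a same-day scan. The schedule also has at least one doubtful tick nearby: clinical observation is marked at screening only, although the narrative places it after the injection ("Following the completion of the injection and clinical observation"). This stands as an unresolved ambiguity. It does not remove the point, because staff who follow the only dated source would scan before day 0, and one edit settles either reading.

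**Exercise before injection.** A reader might infer that participants exercise from screening and that this goes unrecorded. The documents do not support that. Exercise therapy is presented at screening, but nothing says participants start then, and the standardised teaching of the three exercises follows the injection. What can be said is that any exercise before day 0 would not be in the study diary.

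**The 34% figure.** A reader might also infer that a third of the measured change would be spurious. That does not follow. The figure is the corner case of a scan on day −42 and a final visit on day 81, it measures time, and no effect on any estimate has been shown.

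**The fix does not make the change attributable to peppering.** Correct. With a day-0 scan, 81 to 87 days of exercise and natural course remain mixed with peppering, and there is no unpeppered control. That is a separate limitation and adds no weight here. The edit removes only the pre-injection part.

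**No objective depends on it.** Also correct. Ultrasound is in neither objective, and VAS and FFI have day-0 values.

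**Conclusion.** The point holds as a low-cost improvement, with medium confidence. If the schedule is followed, 1% to 34% of the interval between scans lies before the injection, and that interval varies by up to 47 days between participants rather than 6. The before-after change can therefore include change that came before the intervention; its size is unknown and may be nil.

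This rests on two assumptions: that the schedule governs where the narrative gives no day, and that no unscheduled day-0 scan is done. If the narrative was meant to require a same-day scan, what remains is a schedule entry to correct.

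It would be wrong to infer bias in the steroid-versus-saline comparison. The first scan precedes randomisation, so the gap cannot depend on the assigned arm; at most it adds noise.

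**What to change.** Move the initial ultrasound tick from screening to injection day 0, after eligibility is reconfirmed and before randomisation, and state that timing in the baseline list under Interventions and Interactions. If same-day scanning is not practical, scan as close to injection as feasible and record the number of days between scan and injection. A limit of 7 days would serve as an example; that limit is my choice and has no source in the documents.

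No eligibility criterion uses ultrasound, so screening does not need the scan, and the X-ray can stay there. No routine scan is added. The costs are:
- Day 0 becomes longer by one scan, on a visit that already carries examination, questionnaires, dolorimetry, randomisation, injection and exercise teaching. Objective 1a assesses patient and physician time, so this counts there.
- A participant who needs an earlier scan because the diagnosis is in doubt would have a second one.
- For everyone else, an unexpected ultrasound finding would surface on day 0, though still before randomisation.

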Lying within the conservative-surgical treatment spectrum for plantar fasciitis is local corticosteroid injection (CSI) therapy (15), a *minimally invasive intervention* that is relatively quick and easy for the clinician to perform in the *outpatient clinical setting*. A targeted plantar fascia injection typically combines both corticosteroid (CSI) and a local anesthetic (LA) as the substance infused (i.e. *injectate*). Administration of a CSI near the irritated plantar fascia has documented evidence of providing pain relief for up to 1 month only (16). A randomized trial performed as far back as 1956 showed *no statistical difference* between CSI and placebo (i.e., saline) with 6-18 months of follow-up recorded (17). Yet, to this day, a CSI is essentially the only immediate intervention that can be proffered in the outpatient clinic by providers that third-party payers (at least in the United States) will compensate for. In point of fact, 73% of surveyed orthopaedic surgeons *preferred CSI* to treat heel pain (18), *yet* its own preeminent foot association, the American Orthopaedic Foot and Ankle Society (14), advocates for its *judicious* use for fear of deleterious side effects, including fat pad atrophy (20) and possible rupture (21). The ambiguity surrounding corticosteroid *injection* as therapy is further substantiated from histopathologic studies involving plantar fasciitis (22-24), which *failed to demonstrate any inflammatory process*, calling into question the rationale on the use of corticosteroids altogether, which are used primarily for their potent anti-inflammatory effects (18). Reasonably, the terminology plantar *fasciitis* is perhaps a misnomer given the *degenerative* (rather than inflammatory) findings uncovered (24), which some investigators refer to as plantar *fasciosis* or plantar *fasciopathy*, given the similar tissue pathology seen in other musculoskeletal tendon disorders, or *tendinopathies* (25-28, 31).

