While there have been several prospective investigative studies on CSI for plantar fasciitis, there is vagueness on injection method. There are essentially two described techniques (29): single injection (how CSI is traditionally administered) or *peppering* injection, the latter initially described in 1964 (30) as a technique for lateral epicondylitis, a form of chronic tendinopathy involving the arm. Injection *peppering* is thought to disrupt the chronic degenerative process by provoking bleeding and *inflammation* to promote healing (31). Several study trials involving the injection method for lateral epicondylitis highlights that it is the *physical needling of the pathologic site* (i.e. *peppering*) as opposed to the *injectate* that incites healing (30-34). Thus, a *peppering injection* performed for plantar fasciitis, though just hypothetical, would act similarly via repeatedly fenestrating the pathologic site and *opening holes on several spots* rather than a single spot (33) to stimulate hematoma formation and subsequent healing. To our knowledge, only two previous investigative studies have disclosed its use for plantar fasciitis (35, 36). Likewise, the medical evidence on injection therapy for plantar fasciitis also shows imprecision on both the approach (i.e. medial or plantar heel) and target (i.e. superficial to, deep to, or into the plantar fascia) to inject, just as long as it is deposited *close to* the plantar fascia origin (*enthesis*) (19, 25, 37-39). Though ultrasound guidance can provide more real-time accuracy of where the *injectate* infiltrates, it shows no superiority to traditional palpation guided injection therapy (36).

Our research team considers corticosteroid injection a nebulous and insufficient treatment option for plantar fasciitis sufferers. If *first do no harm* is the physician's axiom, then

CSI's continued utilization altogether for this tricky pathology should be questioned. Our investigative team has exposed a knowledge gap and posits a challenge to the existing CSI treatment paradigm for plantar fasciitis via an alternative minimally invasive infracalcaneal peppering injection technique being non-inferior to traditional CSI, with the premise that it is the needle rather than the steroid administered that is beneficial for the patient.

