Successful completion of our proposed pilot study addresses a critical knowledge gap in the treatment of chronic plantar fasciitis and breaches the translational roadblock of clinical implementation. The results from this rigorous pilot study will provide the framework for our anticipated full-scale efficacy trial with the potential of affording the clinician an upgraded evidenced-based treatment option that has been demonstrated to be safe, effective, and reproducible.

Objectives

1. Assess feasibility of infracalcaneal peppering injection technique with and without CSI in the management of patients with chronic plantar fasciitis.
 - a. Feasibility of recruitment, randomization, retention, patient and physician time constraints, and tolerability of treatment will be assessed. Clear quantitative benchmarks and a number needed to treat will be achieved for planned utilization in a subsequent full-scale efficacy trial.
2. Assess the efficacy of infracalcaneal peppering injection with and without CSI for reduction in pain utilizing two validated patient reported outcomes measures (PROMs): the Visual Analog Scale (VAS) and Foot Function Index (FFI), administered at baseline, then at 2, 4, 8, and 12 weeks. Minimal Important Difference (MID) calculations for both VAS and FFI PROMs, specifically for plantar fasciitis, have already been investigated/established and will be used as a reference.
 - a. Greater than 75% of these PROMs from ALL cumulative target dates will be captured, providing a target number needed to treat (NNT) to conduct a full-scale efficacy trial investigation.

Methods and Measures

Design: A randomized, double-blind placebo-controlled pilot study at one single institution

Setting: Atrium Health Wake Forest Baptist Department of Orthopaedic Surgery-Podiatry Services practice located in High Point, North Carolina

Subject Selection Criteria

Inclusion Criteria

- Men and women 18 years of age and older
- Patient reported history of plantar heel pain *and* confirmed clinical tenderness of pain with direct palpation of the medial calcaneal tubercle on baseline exam
- Diagnosis of chronic plantar fasciitis, defined for study purposes as symptoms greater than or equal to 6 weeks in duration

Exclusion Criteria

- Individuals less than 18 years of age
- Pregnancy

- History of receiving a local heel injection (i.e. CSI or other injectate) within the last 3 months
- Prior heel trauma or surgery
- Allergy to local corticosteroid or local anesthesia

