Study Visit #4 – 8 weeks post-treatment intervention	No payment. Next payment at 12-week follow-up study visit (visit #5).
Study Visit #5 – 12 weeks post-treatment intervention	\$40.00

Analytical Plan

Results will be analyzed initially using descriptive statistics. Comparison between groups will be done using chi square tests for proportions, and t-tests or ANOVA procedures for continuous variables. Regression analysis will be performed to identify independent outcome predictors. Other inferential statistical analysis will be conducted as appropriate.

Human Subjects Protection

All patients ages 18 years and up with a diagnosis of plantar heel pain will be screened for inclusion into the study. The study will be conducted in accordance with the current IRB-approved clinical protocol; ICH GCP Guidelines adopted by the FDA; relevant policies, requirements, and regulations of the clinical test site IRB; and applicable federal agencies.

Patients who meet the inclusion criteria will be asked to participate in the research study and provided ample time and encouragement to ask questions and discuss the study with others (medical providers, family, friends, etc.). A copy of the informed consent form will be provided to the patient. The study team will answer all questions.

Subjects may withdraw from the study at any time for any reason at their request. Otherwise, participants will be followed as per the protocol. Attempts will be made to collect clinical data from withdrawn subjects. There will be no replacement of subjects who withdraw from the study.

Subject Recruitment Methods

The study will recruit patients who present to the Atrium Health Wake Forest Baptist Department of Orthopaedic Surgery-Podiatry Services practice located in High Point, North Carolina with symptoms of plantar heel pain. In order to approach patients that have received care at this practice in the past, we will create an i2b2 query to result a list of patients seen by [name] and diagnosed with plantar fasciitis within the last 3 years (11/1/2020 – 11/1/2023). These patients will be contacted by the study coordinator to introduce the study, gauge their interest, and begin the pre-screening process if they opt in to doing so.

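### Objective 2 names no lead outcome or visit, so the efficacy headline stays open until data are seen, and similarity at weeks 8 or 12 alone is weak support for non-inferiority

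*Combined protocol and SAP*

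**What the plan says.** - **Objectives, item 2** sets out to assess efficacy on pain with two instruments, VAS and FFI, "administered at baseline, then at 2, 4, 8, and 12 weeks". It ranks neither instrument and no visit.
- **Evaluation Schedule Summary** lists "VAS PROM (for both general heel pain and first step pain) - FFI PROM" at every visit. The VAS is therefore completed for two kinds of pain, giving three scores per visit if the FFI is taken as one total.
- **Outcome Measure(s)** carries no primary or secondary labels. Its first patient assessment is "Heel Tenderness VAS PROM". No visit collects a VAS under that name, and the general heel pain VAS that every visit does collect is missing from the list. A separate heel tenderness score appears among the physician assessments.
- **Analytical Plan** begins with descriptive statistics and continues: "Comparison between groups will be done using chi square tests for proportions, and t-tests or ANOVA procedures for continuous variables". It then mentions regression for predictors and leaves room for further inferential work. It gives no lead endpoint, visit, significance level, multiplicity rule, baseline adjustment or repeated-measures model.
- **Background text before the Objectives** says that steroid injection has "documented evidence of providing pain relief for up to 1 month only". It frames the hypothesis as an "alternative minimally invasive infracalcaneal peppering injection technique being non-inferior to traditional CSI", on the premise that the needle and not the steroid does the work.
- **Interventions and Interactions** gives both arms the same peppering procedure. Group 1 receives steroid with local anaesthetic, Group 2 local anaesthetic with saline.

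**The concern.** Two separate harms follow.

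The first is selection. With three scores, four visits and a choice between t-tests and ANOVA, nothing fixes in advance which result answers Objective 2. A favourable score and visit could be chosen after the data are seen and carried into the full-scale efficacy trial that this pilot is meant to frame.

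The second is interpretation. The comparison between arms isolates the steroid, because the needling is common to both. If the steroid effect fades after about a month, the arms may look alike at weeks 8 and 12 whether or not needling helps. With no visit named, a late non-significant difference could be offered as support for the non-inferiority premise. A family-wise error rate does not measure this second harm, so it needs its own safeguard.

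**Working it through.** **Inputs.** Three scores and four post-injection visits (Objectives item 2; Evaluation Schedule Summary). 50 participants (Sample Size) allocated 1:1 (Interventions and Interactions), so 25 per arm. The plan states no significance level, so two-sided 5% per test without adjustment is assumed. It states no correlations, so a range is shown.

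**The plan's own figure.** The only stated figure is the total of 50. It cannot be reproduced, because no power, effect size, SD, margin or dropout rate is given.

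**Number of comparisons.**
- Each score t-tested at each visit: 3 × 4 = 12, of which 3 × 2 = 6 fall at weeks 8 and 12.
- One repeated-measures group test per score: 3.

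The plan does not say which applies.

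**Chance of at least one false positive when the arms do not differ.**

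| Reading | Independent | Assumed common correlation 0.3 / 0.5 / 0.7 |
|---|---|---|
| 12 tests | 1 − 0.95^12 = 46.0% | about 39% / 32% / 23% (simulated) |
| 3 tests | 1 − 0.95^3 = 14.3% | 13.5% at 0.3, falling to 10.9% at 0.7 |

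A second simulation used actual two-sample t-tests with 25 per arm and separate correlations between scores and between visits, each from 0.3 to 0.8. It gave 42.6% down to 21.8% for the 12 tests, so the range does not depend on assuming one common correlation.

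**What a non-significant result can show.** With 25 per arm and no losses, the standard error of an unadjusted difference is √(2/25) = 0.283 SD. The 95% CI half-width is about 1.96 × 0.283 = 0.55 SD. For a true difference of 0.5 SD, power is 42.4%, so 100 − 42.4 = 57.6% of such trials would find no significant difference. Non-significance is therefore not evidence of non-inferiority at any visit.

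**What timing adds.** Weeks 2 and 4 fall within or at the edge of the month for which the background reports relief; weeks 8 and 12 fall outside it. Choosing repeated measures does not remove the problem. As an illustration, if the steroid difference were d at weeks 2 and 4 and zero later, the average over visits would be (d + d + 0 + 0)/4 = d/2.

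**The case against.** The strongest reply is that this is a pilot. Feasibility is Objective 1, the analysis starts with descriptive statistics, and the only numerical target for the patient-reported outcomes is capture above 75%. A pilot need not have a confirmatory efficacy test, and labelling every efficacy comparison exploratory would resolve much of the problem. This stands as a reason for moderate severity. It does not remove the point, because Objective 2 claims to assess efficacy and the Analytical Plan provides inferential tests for doing so.

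Several stronger readings are tempting, but the documents do not support them:

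- **That the plan commits to at least 12 tests.** It also allows ANOVA and does not call for testing visit by visit. Twelve is one reading and three is another.
- **That the protocol expects no steroid effect at weeks 8 and 12.** The one-month statement is background evidence on steroid injection in general, not a prediction for this trial. The needle-not-steroid premise applies to every visit.
- **That the late visits cannot discriminate.** The background proposes that needling promotes healing and cites possible steroid harms, so a late difference in either direction is possible and would be informative. Later visits also bear on durability.
- **That a false non-inferiority rate can be computed across all visits.** The plan gives no margin or level. Placing the truth at the margin at every visit would contradict the argument that the arms may be alike late on.
- **That the text dictates first-step pain at week 4.** Nothing ranks that score first. Week 4 ± 3 days spans days 28 − 3 = 25 to 28 + 3 = 31, the edge of the one-month window, and week 2 lies more clearly inside it.

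**Conclusion.** The concern holds in a limited form and should be addressed. No lead outcome, lead visit or multiplicity rule appears anywhere in the document, so the efficacy headline is not fixed before the data are seen. The risk of at least one false positive is 46% for 12 independent tests, about 23% to 39% for 12 tests at correlations of 0.7 to 0.3, and 14.3% for 3 independent tests. These figures rest on an assumed two-sided 5% level, assumed correlations and one FFI total per visit.

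Similarity at weeks 8 or 12, taken alone, is weak support for the non-inferiority premise, because any steroid effect may have worn off by then. That rests on the protocol's own summary of the evidence and on the arms differing in the steroid. It does not make those visits uninformative. The mismatch between the VAS named in Outcome Measure(s) and the VAS collected at the visits is a plain inconsistency.

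**What to change.** Before unblinding, amend Outcome Measure(s) and the Analytical Plan as follows:

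1. Name one lead efficacy contrast: one patient-reported score at one visit within the first month. First-step pain VAS at week 4 is an example; the team should choose and justify its own.
2. Analyse it with adjustment for the day-0 score, which is already collected. Report the between-arm difference with a 95% CI against the MID, in place of a t-test p-value. State the MID value to be used, since the plan refers to it without giving a number.
3. Report all other score-by-visit comparisons, and those of pressure threshold, heel tenderness score and ultrasound, as exploratory estimates with CIs and no significance claim.
4. State that a non-significant difference at any visit, including weeks 8 and 12, will not be read as non-inferiority.
5. Reconcile the "Heel Tenderness VAS PROM" entry with the general heel pain VAS collected at every visit.

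The cost is a few sentences of protocol text, with no new data, visits or participants. The small downside is that results on other scores or at other visits can no longer be headlined.
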